12.0 Provisions to Monitor the Data to Ensure the Safety of Subjects

12.1 Data and Safety Monitoring Plan

The purpose of the data and safety monitoring plan is to establish standards that will ensure that this protocol complies with Federal Regulations, Health Insurance Portability and Accountability Act (HIPAA) requirements, and applicable Dana-Farber Harvard Cancer Center (DF/HCC) Standard Operating Procedures.

General Approach: We have developed a comprehensive data and safety monitoring plan for the proposed project. Throughout the award period, weekly meetings will take place with the research team: [name] and [name], and study staff (clinical research coordinator [CRC] and interventionist). Specifically, meetings will include ongoing review of study protocol, assessment procedures, and issues related to recruitment, data collection, and management. Study staff will also discuss any human subject issues that arise.

General Roles and Responsibilities: We will use several coordinated strategies to monitor study recruitment, enrollment, and retention, as described in the following table. We will also closely track collection of patient-reported assessments, as these measures are an essential aspect of our study procedures and outcomes. For all strategies identified in the table, we will develop study tracking forms that will be reviewed at the weekly team meetings. Study tracking forms will be used to create a record of all decisions made and actions taken. I will send a report ahead of the meeting detailing study progress and setting the agenda. The following monitoring and reporting steps will be taken for each study activity:

Study Activity	Monitoring and Reporting Mechanism
Recruitment	
• The designated CRC will generate a weekly report outlining the number of patients approached and reasons for ineligibility or

	disinterest in study participation
Informed Consent	
 • The CRC will generate a weekly report detailing the number of participants who signed informed consent. • The PI will go through any issues related to informed consent with the CRC weekly or earlier if urgent
Enrollment	
 • The CRC will generate a weekly enrollment report
Assessments	
 • The CRC will conduct a review for completeness and accurate data entry. • The CRC will conduct regular checks of MEMS Caps adherence data and contact patients once in the initial set-up to verify use of MEMS Caps. • The CRC will maintain participant records of distress levels at each timepoint and follow Reaction Management if required.
Intervention	
 • The CRC will contact patients to test the videoconferencing technology. • The PI and [name] (Study Co-Investigator, PI Co-Mentor) will review at least 10% of audio-recorded treatment sessions. • The CRC will maintain a record of participant progress in sessions, including attendance.
Retention	
 • The CRC will generate a weekly report detailing completion of follow-up assessments and retention strategies implemented for each participant. • The CRC will generate a weekly report of all participants who withdraw from study.
Analysis	
 • The PI will work closely with study biostatistician, [name] (scientific advisor in biostatistics), on all qualitative and quantitative analyses.

Specific PI Roles and Responsibilities

I will be responsible for all aspects of conducting the protocol; I will:

- Oversee the coordination, development, submission, and approval of the protocol to the DF/HCC as well as subsequent amendments.
- Ensure that the investigators and study team members are qualified and appropriately resourced to conduct the protocol.
- Carry out a Data and Safety Monitoring Plan as detailed in this document.
- Ensure that each participating study team member receives adequate protocol training prior to enrolling participants and throughout the trial's conduct as needed.
- Monitor progress and overall conduct of the study.
- Conduct review of 10% of intervention sessions for process and content fidelity.
- Conduct weekly supervision for clinical protocol interventionists.
- Review data and maintain timely submission of data for study analysis.
- Ensure compliance with all requirements as set forth in the Code of Federal Regulations, DF/HCC, HIPAA requirements, and the approved protocol.
- Commit to provisions that the protocol will not be rewritten or modified by anyone other than the overall PI.
- Monitor accrual and address concerns if accrual goals are not met.

The Massachusetts General Hospital Cancer Center is expected to comply with all applicable federal regulations and requirements, the protocol and HIPAA requirements. Specifically, it will:

- Oversee the data collection process.

- Maintain documentation of Serious Adverse Events (SAE) reports and deviations/violations.
- Maintain regulatory documents which include but are not limited to the following: IRB approvals/notifications, confirmation of Federalwide Assurances (FWAs), all SAE submissions, screening logs, and IRB approved consents.
- Conduct regular communications with the PI and maintain documentation of relevant communications.
- Document the delegation of research specific activities to study personnel.
- Maintain regulatory files.
- Have office space, office equipment, and internet access that meet HIPAA standards.
- Participate in quality assurance activities and meet with monitors or auditors at the conclusion of a visit to review findings.
- Promptly provide follow-up and/or corrective action plans for any monitoring queries or audit findings.

Informed Consent Requirements. The DF/HCC approved informed consent document will serve as a template for the informed consent.

Protocol Confidentiality. All documents, investigative reports, or information relating to the participants are strictly confidential. Confidentiality is assured as participants will be identified on all study materials only by participant number, visit number, and date of visit. By recording the study data in this manner, the information can be considered 'de-identified,' and therefore compliant with the Standards for Privacy of Individually Identifiable Health Information ("Privacy Rule") of HIPAA. Participants data will be kept in a computer file that is password protected and this password will be changed whenever the staff changes. This password-protected file will be stored on the encrypted MGH network drive on hospital computers. Only the Principal Investigator and study staff will have access to the data. We will keep a link between participant number and participant's name in a separate file, also password protected (with a different password).

Data Management Organizational Structure Data. Study forms will undergo a systematic and rigorous editing process prior to being keyed into the database. The research assistant will routinely evaluate the data and discuss any problems and questions with the study staff, myself, and mentors at the regular weekly team meetings. Data management formal reports on record status across the three following domains will be employed: entered, verified, and edited. These reports of data records will be evaluated once a month during the final team meeting of the month. All study data (including data from the Electronic Health Record) will be stored on the encrypted MGH network drive on hospital computers and will be password protected. To ensure data protection, backup copies automatically generated by MGH computer systems will be available.

Data Safety and Monitoring Plan. The following procedures will be followed, in compliance with NIH requirements, to ensure the safety of study participants and the validity and integrity of data:

- Data Repository: The MGH Cancer Outcomes Research Program (CORe) has coordinated research initiatives over the past ten years that have established procedures and technologies for data collection and management. I will oversee all aspects of data collection for the study and the research assistant will have the operational responsibility of data management. We will develop a study specific data management protocol and standard operating procedures for the creation and testing of all study forms, data collection, quality control, and data extraction. These forms will be standardized. We will provide ongoing oversight of data management throughout the study, and will be responsible for generating reports and datasets for quality control and data analysis. All data management activities will utilize REDCap, a HIPAA-secure, web-based survey application for electronic collection and management of research and clinical trial data. REDCap data collection projects rely on a thorough study-specific data dictionary defined in an iterative self-documenting process by all members of the research team with planning assistance from Partners HealthCare Research Computing, Enterprise Research Infrastructure & Services (ERIS) group. REDCap provides an intuitive interface for users to enter data and have real

time validation rules (with automated data type and range checks) at the time of entry. Data management reports will be generated weekly and discussed during the study team meetings.

- **Serious Adverse Events:** Expedited review will occur for all events meeting the Food and Drug Administration (FDA) definition of a SAE (i.e., any fatal event, immediately life-threatening event, permanently or substantially disabling event, event requiring or prolonging inpatient hospitalization, Unanticipated Problems [UPs], or any congenital anomaly). This also includes any event that a study investigator judges to impose a significant hazard, contraindication, side effect, or precaution. For purposes of this study, all SAEs will be required to be reported to the PI, the DF/HCC IRB, and federal agencies (National Cancer Institute, FDA, and the NIH Office of Biotechnology Activities), regardless of any judgment of their relatedness to the study. All relevant information will be reported to the study investigators for each SAE including information about the event and its outcome, study condition, concomitant medications, the subject's medical history and current conditions, and all relevant laboratory data. Notification by secure e-mail of all related study forms shall be made to the DF/HCC IRB within 24 hours of the occurrence of any SAE. Information will be reviewed and a determination made of whether there was any possible relevance to the study interventions. Reporting to NIH will be made according to their respective regulations governing SAE reporting.
- **Non-Serious Adverse Events:** At weekly meetings, the research team will discuss summaries of the numbers and rates of adverse events by treatment group. These reports will include types of events, severity, and treatment phase.
- **Other Safety-Related Reports:** At weekly meetings, the research team will discuss summary reports of treatment retention and reasons for dropout or withdrawal by treatment group.
- **Study Stopping Rules:** We do not have a pre-specified stopping rule given the low-risk nature of the proposed study. However, if at any point the DF/HCC or the study investigators judge that the risks of study procedures outweighs the benefits, the project will be stopped immediately.
- **Procedures to ensure confidentiality, preparation of reports, minutes, and recommendations:** We will work with the CRC to prepare study reports and circulate them to research team during the weekly scheduled project meetings. These reports will include overall study progress and safety data. At the conclusion of each research group meeting, the investigators will determine whether any changes in the conduct of the trial are recommended.

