STRIDE Intervention. The intervention content is included in Appendix 30.11. STRIDE is a brief, group-based, videoconference intervention with six weekly one-hour sessions and two follow-up 15-30-minute phone check-ins at month four and five. The STRIDE intervention incorporates aspects of *CBT for Adherence and Depression*,⁴¹ employing symptom management, cognitive restructuring, behavioral activation, and skills-based methods to address adherence and psychiatric symptoms. The first three sessions entail an assessment of patient, treatment, and healthcare system/provider barriers to adherence, followed by psychoeducation about breast cancer risk and benefits and risks of AET. We will employ specific interventions to target patient-identified barriers. For example, cognitive reframes will be applied to optimize accuracy related to recurrence risk perception and clinical necessity for therapy. Problem-solving will be implemented for management of financial distress (e.g., develop plan with social work and oncology team). To target healthcare system/provider barriers, the protocol will teach assertiveness skills for adopting an active role with clinicians and increasing self-efficacy. The last three tailored sessions will target treatment factors; patients will receive training in symptom management and coping strategies specific to the side effects or symptoms that they endorse. CBT is effective in helping patients manage cancer-related side effects such as pain, fatigue, and menopausal symptoms such as hot flashes. CBT strategies will address individual sources of distress, such as difficulty managing symptoms, or financial concerns around medication cost that are interfering with adherence and exacerbating distress. In extenuating circumstances, participants may be scheduled for individual sessions if we cannot schedule them for a group session within a reasonable amount of time.

Participants in the STRIDE intervention will continue to monitor medication-taking with the MEMS Caps throughout the 24-week study period. As part of the intervention, participants will practice relaxation training using study recordings through the study's website portal

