(stridestudy.mgh.harvard.edu). The structure of each website post can be viewed in Appendix 30.25. The website will move into production after IRB approval. This is a website created with the support of IT at MGH/HMS and is viewable to those with the link to the website URL. The website will contain no advertisements or other content. It will only contain the relaxation file, and the individual sessions from the work book that the intervention participants receive, so that they can also have an electronic version accessible for the future. Study staff will provide instructions for participants to access this website via email as part of the intervention session reminders (Appendix 30.14). In addition to the overall study PI, [name], trained clinical psychology practicum students, clinical psychology fellows, licensed psychologists or social workers on the study team at MGH will deliver the intervention, to ensure successful administration of the intervention. Interventionists will complete a post-intervention survey for each group intervention, which will document process variables such as session length, session interventionist, and session attendance. [name] has ample experience delivering this type of intervention and was a protocol therapist on several NIH-funded CBT-based studies. She will conduct weekly clinical supervision with trained interventionists. 80% of sessions will be audio-recorded and at least 10% randomly selected, stratified by interventionist, and reviewed with [name] for treatment fidelity. Content fidelity will be assessed by calculating the percentage of key intervention topics addressed out of total topics, with a goal of 90%.⁵¹ Feedback will be given to interventionists to enhance adherence to the protocol.

Finally, participants who identify as part of a racial/ethnic minority population will be offered the opportunity to participate in a qualitative exit interview to provide feedback on the STRIDE program.

Medication Monitoring Control. Participants in the comparison condition will not receive the STRIDE intervention; however, they will monitor medication-taking with MEMS Caps and undergo standard care with oncology follow-up.

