14.0 Risks to Subjects

14.1 Reporting Adverse or Unanticipated Events

We do not anticipate any harm with our study procedures. While some topics probed in study assessments and the STRIDE Intervention may be sensitive in nature, no adverse or unanticipated events occurred in previous studies of psychological interventions conducted by our research group. Reportable adverse events would include a breach of confidentiality. Should adverse or unanticipated events occur during the study, a trained study staff member will report the events to the IRB as soon as they are discovered.

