14.2 Anticipated Reaction

As this is a low-risk, social/behavioral study, there are no ingested medications, and no biomedical procedures. It is unlikely that participants will be at any risk for physical harm because of study participation. Participants may find some of questions in the questionnaire or

content in the intervention to be emotionally upsetting, and if so, they may experience some distress.

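### Adverse-event rates are to be summarised by arm, but no question or schedule elicits events equally in both arms, so the rates may differ through contact alone

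*Combined protocol and SAP*

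**What the plan says.** Section 12.1 (Non-Serious Adverse Events) states that "the research team will discuss summaries of the numbers and rates of adverse events by treatment group", and adds: "These reports will include types of events, severity, and treatment phase". The Serious Adverse Events item in 12.1 counts any event that requires or prolongs an inpatient stay and asks for all such events regardless of relatedness. Notification "shall be made to the DF/HCC IRB within 24 hours of the occurrence of any SAE".

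Section 14.1 says of adverse or unanticipated events that "a trained study staff member will report the events to the IRB as soon as they are discovered". Its one example is: "Reportable adverse events would include a breach of confidentiality". Section 14.2 recognises that women may find questionnaire items or "content in the intervention to be emotionally upsetting, and if so, they may experience some distress".

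On contact, Section 9.2 gives STRIDE "six weekly one-hour sessions and two follow-up 15-30-minute phone check-ins at month four and five". For the other arm, "Participants in the comparison condition will not receive the STRIDE intervention"; controls use the MEMS cap and have standard oncology follow-up. Both arms complete questionnaires at 12 and 24 weeks (Section 9.3).

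**The concern.** A rate by arm means something only if events are looked for in the same way in both arms. Here the plan promises the rate, with type and severity, but schedules no source for it:

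- Table 3 has no adverse-event row and marks chart review under screening only.
- The EHR items in Section 9.3 are covariates, and hospital stays are not among them.
- The questionnaires in Appendix 30.17 do not ask about hospital stays or harm from taking part.
- The appendix list in Section 30.0 contains no adverse-event form.
- The interventionists' survey in Section 9.2 is described by process variables such as session length and attendance.
- No severity scale or look-back period is given.

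Most events would therefore reach the team only when a woman mentions them. STRIDE women have many more occasions to do so, in live conversation about side effects and distress. An excess of events in STRIDE could reflect nothing but that.

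The summaries have a use. Under 12.1 the investigators decide after each meeting whether to recommend changes to trial conduct, from reports that include safety data. There is no pre-specified stopping rule, so stopping rests on a judgement of risk against benefit.

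**Working it through.** The plan states no adverse-event rate or contact count, so there is no figure of its own to reproduce.

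**1. Contacts after baseline**

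| Count | STRIDE | Control |
|---|---|---|
| Sessions (9.2) | 6 | 0 |
| Check-in calls (9.2) | 2 | 0 |
| Assessments (9.3) | 2 | 2 |
| Subtotal | 10 | 2 |
| With MEMS set-up contact (12.1) | 11 | 3 |
| With videoconference test (12.1; STRIDE only, by its purpose) | 12 | 3 |

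A woman who attends 4 of 6 sessions has 4 + 2 + 2 = 8 contacts against 2, or 9 against 3 with the set-up contact. Reminders around each assessment (9.4) are not counted.

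**2. Allowing for timing.** A contact can reveal only events that have already happened. Assume that events fall evenly over 24 weeks, sessions start in week 1, 3 or 6, calls come in weeks 17 and 21, and assessments in weeks 12 and 24. A contact in week t follows a fraction t/24 of events, so the mean number of later contacts per event is the sum of t divided by 24. Set-up contacts come near week 0 and add almost nothing.

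- Control: (12 + 24)/24 = 1.5.
- STRIDE, start week 1: (21 + 17 + 21 + 12 + 24)/24 = 95/24 = 4.0.
- STRIDE, start week 3: (33 + 74)/24 = 107/24 = 4.5.
- STRIDE, start week 6: (51 + 74)/24 = 125/24 = 5.2.

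The ratio runs from 4.0/1.5 = 2.6 to 5.2/1.5 = 3.5.

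**3. Illustration with equal true risk.** Let each later contact reveal an event with an assumed probability p. An event with k later contacts is found with probability 1 − (1 − p)^k, averaged over event times. For controls, events in the first 12 weeks have k = 2 and later ones k = 1. At p = 0.1 this gives 0.5 × 0.19 + 0.5 × 0.10 = 0.145. For STRIDE starting in week 1, k falls from 10 to 1 over intervals of 1, 1, 1, 1, 1, 1, 6, 5, 4 and 3 weeks.

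| p | STRIDE, found per 10 events | Control, found per 10 events | Ratio |
|---|---|---|---|
| 0.1 | 3.2 to 3.9 | 1.45 | 2.2 to 2.7 |
| 0.2 | 5.3 to 6.0 | 2.8 | 1.9 to 2.1 |
| 0.4 | 7.8 to 8.1 | 5.2 | about 1.5 |

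If half of events were caught equally in both arms by other routes, then at p = 0.2 the ratio would be (0.5 + 0.5 × 0.53)/(0.5 + 0.5 × 0.28) = 0.765/0.64 = 1.2, or 0.80/0.64 = 1.25 with the later session start.

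The illustration gives a one-hour session and a questionnaire the same p. Questionnaires that do not ask probably reveal less, which would widen the gap; shared routes narrow it.

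**4. Reporting clocks side by side.** Section 12.1 counts 24 hours from when a serious event occurs. Section 14.1 reports events on discovery. Section 14.3 allows 72 hours, from completion online or from receipt on paper, to check a distress assessment and notify the principal investigator. An event first learned from a returned assessment can be handled within 14.3 and still miss the limit in 12.1.

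**The case against.** The case on the other side is substantial, and several stronger readings fail against it.

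- **A reader might infer that nothing collects adverse events.** That is not so. Staff review every assessment for distress in both arms, with a call when the even-numbered HADS items reach 11 (14.3). The coordinator keeps distress records at each timepoint (12.1). Women who withdraw are asked why, so that serious events are not missed (13.0). The BCPT and FACT-B ask about symptoms in both arms, and study forms and procedures are still to be written (12.1). But the HADS rule concerns depression scores, the withdrawal query reaches only women who leave, and neither symptom scale is designated as a safety source. None of these would find a hospital stay in a woman who remains in the study.
- **A reader might infer a five-fold excess from 10 contacts against 2.** That would let contacts reveal events that have not yet happened, and it omits the set-up contact.
- **A reader might infer a formal comparison, or safety evidence for the full-scale trial.** Section 12.1 describes a monitoring summary. Adverse events are not an endpoint in Section 8.0 and have no analysis in Section 11.1. That section carries forward effect sizes, feasibility and acceptability.
- **A reader might infer that 14.1 limits adverse events to confidentiality breaches.** Its wording gives an example, not a closed list. HADS change between groups is already an exploratory endpoint.
- **The reporting clocks.** Section 14.1 covers adverse and unanticipated events in general, whereas 12.1 covers serious ones. Inevitable breach follows only from a strict literal reading of 12.1.

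It is also fair that this is a low-risk behavioural pilot whose primary endpoints are feasibility and acceptability, which this point leaves untouched.

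**Conclusion.** The point holds in limited form. The plan promises by-arm adverse-event rates without a source that elicits events or hospital stays equally in both arms. With about 10 to 12 contacts against 2 to 3, or about 4 to 5 against 1.5 once timing is allowed for, the rates may differ when the true risks are equal. The likely direction is higher in STRIDE. The size is unknown: it depends on the chance that a contact reveals an event, which the documents do not give, and on how much the shared routes catch. The timing figures rest on evenly spread events, assumed contact weeks and full attendance.

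Separately, the time limits in 12.1, 14.1 and 14.3 do not fit together. No primary or secondary conclusion is affected. This is an inexpensive improvement to safety monitoring and a set of rules to reconcile.

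**What to change.** In Section 12.1 and Table 3:

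1. Add one identical adverse-event and hospitalisation item, with a stated look-back period, to the 12- and 24-week questionnaires in both arms. If the EHR permission covers it, add a chart check for hospital stays at the same two times.
2. Base the by-arm summaries only on these common sources. List events volunteered in sessions or calls separately. Such events would still be reported as the protocol requires.
3. Add to the by-arm safety summary the number of women who newly meet the protocol's existing HADS criterion in 14.3 at 12 and 24 weeks. This uses data already collected in both arms and covers part of the distress anticipated in 14.2.
4. Reconcile the serious-event clock in 12.1 with the discovery wording in 14.1 and the 72-hour allowance in 14.3, so that staff can follow all three.

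The cost is one questionnaire item, up to two short record checks per woman by existing staff, and an amendment. Section 13.0 implies continuing EHR access, but permission for this use should be confirmed. The downside is that more unrelated events will be found and reported in both arms.
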